6.1.2 Two weeks Run in period

Following the initial screening visit (Visit 1) subjects consented for the study will enter a two week run in period. There should be no changes to treatment or lifestyle in this period.

- Subjects who fail to meet the eligibility criteria at the end of the run-in period will be withdrawn from the study.
- Subjects who meet eligibility criteria and are deemed stable at the end of the run-in period will be assigned in random order to two weeks on ambulatory oxygen or no treatment for two weeks during the baseline visit.

6.1.3 Baseline Assessments – Visit 2 in Week 0

After the two weeks 'run in period' patients will return to the clinic to attend the baseline visit (study Visit 2 in Week 0).

Patient will be asked to complete the K-BILD (14) questionnaire in addition to other questionnaires (the Shortness of Breath Questionnaire (SOBQ (15)), St George's Respiratory Questionnaire (SGRQ) (16), Hospital Anxiety and Depression Scale (HDAS)(17,18)), and to perform two 6MWTs, one on oxygen and one on air-filled canisters at the flow rate identified during the screening visit, in random order, with a rest of at least 30 minutes between tests. The patient will be blind to the content of the canisters.

Measured parameters will include 6-minute walk distance, oxygen saturation and heart rate measured continuously (WristOx2™ model 3150), Borg dyspnoea and fatigue score before and at the end of the test, time to recovery of heart rate, oxygen saturation, Borg dyspnoea and fatigue. These parameters will be related to any changes in the primary and secondary outcome variables in the current trial, to identify any baseline predictors of responsiveness.

Only patients with stable respiratory symptoms at baseline visit (no changes in medications and no chest infections during the four weeks before the baseline visit including the run in period) will be randomized into the study as outlined in Section 9.2.

6.1.4 Ambulatory Oxygen crossover Trial procedure

This study is a randomized crossover trial of ambulatory oxygen for use during physical activity. Patients meeting eligibility criteria and deemed clinically stable at the end of the run in period, will be assigned in random order to two weeks on ambulatory oxygen or not during the baseline visit. Optimal oxygen flow rates will be determined during the screening visit on the basis of the entry 6MWT on O₂, so as to maintain oxygen saturation ≥ 90 for at least half of the 6MWT, where possible. Following receipt of the treatment arm assigned during the baseline visits for two weeks patients will cross-over to receive the alternative treatment for further two weeks.

6.1.5 Ambulatory Oxygen Unit

Portable oxygen can be delivered by a variety of devices, differing in weight and size. For the purposes of this study, in order to standardize delivery and taking into account availability across oxygen company contractors, the light-weight portable oxygen gas cylinders will be used across sites to standardise mode of delivery. More information is provided in Section 13 of the study protocol.

[figure not shown]
6.2 Dosage regimen and rationale

This is a short trial as oxygen has immediate effect. The short duration was also chosen to minimise the possibility of changes to the disease status or use of other drugs, and therefore to minimize background variation in potential confounding factors. Oxygen flow rates will be determined on the basis of the entry 6MWT on O₂, so as to maintain oxygen saturation ≥ 90 for at least half of the 6MWT, where possible.

6.3 Concomitant treatment

It will be possible to introduce any rescue medication during the study period as judged appropriate by the treating physician. The aim is to enrol subjects whose treatment is not expected to change during the four weeks treatment period of the trial. Patients who are on established treatment for their IPF or other Fibrotic Lung Disease (FLD), with immunosuppressants, corticosteroids, NAC and Pirfenidone will continue on their regular medication. Concomitant medication will be recorded in patient's notes and the Case Report Form (CRF).

6.4 Schematic of trial design

7 Eligibility criteria

7.1 Inclusion criteria

- i. Patients with a diagnosis of IPF, or with another fibrotic ILD (including fibrotic non-specific interstitial pneumonitis, fibrotic organising pneumonia and fibrotic hypersensitivity pneumonitis) according to established guidelines.

- ii. Patients aged 18 - 99 yrs.
- iii. Patients whose oxygen saturation (SaO₂) at rest on room air is ≥94% and falls ≤ 88% on a baseline 6MWT (performed as part of their routine assessment);
- iv. Patients with stable symptoms (no changes in medications and no chest infections) and treatment during the period of four weeks prior to being randomised into the study, including the two week run in period.

7.2 Exclusion criteria

- i. Patients expected to change treatment over the time course of the study, and those meeting criteria for long term oxygen therapy, *i.e.* hypoxic at rest (Oxygen Saturation at rest on room air <94%).
- ii. .
- iii. Patients with connective tissue disease-associated ILD or with sarcoidosis with musculoskeletal/joint involvement/symptoms will be excluded due to the potential impact in relation to day-to-day mobility.
- iv. Patients with significant communication or other locomotor difficulties, and/or severe co-morbidities.
- v. Current smokers in view of the potential risks associated with use of supplemental oxygen.
- vi. Pregnancy.
- vii. History of symptomatic ischaemic cardiac disease (exertion-induced chest pain).
- viii. Anaemia, Hb < 9g/dl.

8 Subject/Patient Recruitment process

Patient recruitment at a site will only commence once the trial team has ensured that the following approvals/essential documents are in place:

1. The main REC, and Clinical Trial Authorization (CTA) approval,
2. Final sponsorship and/or NHS Permission (previously known as R&D approval),
3. Sponsor has conducted the trial initiation procedure
4. Local Site Delegation of Duties and Signature Log is completed.

All sites participating in the trial will also be asked to provide a copy of the following:

1. Signed Clinical Trial Site Agreement (CTSA),
2. Host site (R&D approval) and/or NHS Permission
3. Signed Delegation of Duties and Responsibilities Log.

9 Study procedures

9.1 Informed Consent procedure

Informed consent will be obtained by the Principal Investigator (PI) and co-Investigators in the collaborating sites, and/or nominated deputies, including a Research Nurse or an ILD clinical research fellow, as recorded on Sponsor's Delegation of Responsibilities Log. Only those members of the study team who have clinical responsibility for the care of patients under the care of the general medical service will be permitted to seek informed consent. All individuals taking informed consent will have received training in Good Clinical Practice (GCP).

The potential participants will be approached in clinic by their usual care team and if they agree, they will then be approached by a member of the research team and they will have the study explained verbally and be given written information (a copy of the PIS) to take away and allowed time to consider whether to join the study. They will then be telephoned to ask if they wish to join.

Alternatively, a Patient Information Sheet (PIS) will be posted to the patient before consenting or given to them on the day of consent, at their clinical appointment. Sufficient time will be given to the patient to allow them to read the information and formulate any questions. They will then be approached at their clinic visit or by telephone to ask whether they would like to join the study.

The research clinical fellow and/or nurse and clinical team will work in conjunction to identify suitable patients. Patient records will not be accessed without the permission of the clinical team responsible for the patient.

Consent to enter this study will be obtained after a full account has been provided of its nature, purpose, risks, burdens and potential benefits, and the patient has had the opportunity to deliberate. The patient will be allowed to specify the time they wish to spend deliberating, usually up to 24 hours.

Periods shorter than 24 hours will be permitted if the patient feels that further deliberation will not lead to a change in their decision, and provided the person seeking consent is satisfied that the patient has fully retained, understood and deliberated on the information given. This provision has been made with the support of our patient advisory group.

Likewise, periods longer than 24 hours will be permitted should the patient request this. The Investigator or designee will explain that the patients are under no obligation to enter the trial and that they can withdraw at any time during the trial, without having to give a reason.

A copy of the signed Informed Consent Form (ICF) along with a copy of the most recent approved Patient Information Sheet (PIS) will be given to the study participant. The original signed consent form will be retained at the study site (one filed in the patient's medical notes and one filed in the Investigator Site File (ISF)). A copy of the consent form will also be given to the patient.

If new safety information results in significant changes to the risk–benefit assessment, the consent form will be reviewed and updated if necessary. All subjects, including those already

being treated, will be informed of the new information, given a copy of the revised consent form and asked to re-consent if they choose to continue in the study.

9.2 Randomisation procedure

All study patients will be randomized twice during the baseline study visit:

1. Randomisation as to the order in which subjects will perform the 6MWT on oxygen *versus* air. The patients will be blind to the content of the canister.
2. Randomisation as to the order in which subjects will have the portable home oxygen *versus* no oxygen during the first two weeks of treatment.

The Trust Statistician, [name], will provide a master randomization list that will form basis of the study randomization *via* an InForm database set up by Imperial College Clinical Trials Unit (ICTU).

9.3 Emergency un-blinding

Emergency un-blinding is not applicable to this study. Even though the patient will be blinded while undertaking the 6MWT on oxygen or air, the investigator will not be blind to the content of the canister.

The air or compressed oxygen used during the 6MWT are not considered to be study IMPs or NIMPs.

10 Study Assessments

10.1 Timing of Assessments

The schedule for study visits including the assessments and procedures to be performed is presented in Table 2 Schedule of events table. The scheduled study visits should occur at the specified week post-screening \pm 7 days unless otherwise specified.

The primary outcome will be the change in the King's Brief Interstitial Lung Disease (K-BILD) total health status score (14). The K-BILD is a questionnaire developed and validated specifically for patients with ILD, using a cohort of 173 ILD patients attending the Royal Brompton Hospital (RBH) and King's College Hospitals (KCH) in London.

The K-BILD asks patients to rate the impact of their ILD in the previous 2 weeks. It is a simple, brief, and easy to complete questionnaire containing only 15 questions, relating to three domains: breathlessness and activities, psychological and chest symptoms. Patients are asked to rate the severity of the impact of their ILD on each of 15 items, on a scale from 1 to 7.

Repeatability (measured 2 weeks apart in patients with clinically stable ILD) is high, with an intra-class correlation coefficient of 0.94 for the total score ("health status" score), and of 0.96 for breathlessness and activity domains.

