10.2 Screening assessments at Visit 1 (Week -2)

Patients with fibrotic ILD will be screened during their routine outpatient/inpatient assessment.

As part of routine clinical care, all patients will undergo:

- Physical examination (including demographics past and current medical history);
- Blood pressure;
- Pulse oxymetry at rest on room air;
- Spirometry and Echocardiogram
- Concomitant medication review;
- 6 Minute Walk Test (6MWT) - patients who desaturate $\leq 88\%$ on room air (RA) will have a repeat 6MWT on ambulatory oxygen, to assess optimal flow (7). 6MWT measured parameters will include 6-minute walk distance, oxygen saturation and heart rate Borg dyspnoea and Borg fatigue score before and at the end of the test, time to recovery of heart rate, oxygen saturation, Borg dyspnoea and Borg fatigue score, acceptable also +/- 1 week.;
- Collection of blood for laboratory analysis including BNP level. BNP levels are acceptable within +/- 1 month from visit 1;
- Pregnancy test (for women of child bearing potential).

Historical evidence will be acceptable for the purpose of study screening only if it was conducted within the timelines given below:

- The echocardiogram and the spirometry will be accepted if performed within 6 months before screening visit (visit 1). Where either of the assessments are not available as part of routine medical care the assessment should be booked to take place within 6 weeks post visit 1.
- The 6MWT will have to be performed at the screening visit +/- one week.
- BNP levels are acceptable within +/- 1 month from the visit 1.

Patients who desaturate $\leq 88\%$ will have a repeat 6MWT on ambulatory oxygen, to identify the oxygen flow needed to maintain optimal saturation ($\geq 90\%$, for at least half of the 6MWT duration, where possible) (7).

Patient should rest for at least 20 minutes between walks. The initial amount of oxygen offered will be calculated depending on level of desaturation during 6MWT on room air, as follows:

- Saturations 88-86% - start with 2 litres,
- Saturations 86-83% -start with 3 litres,
- Saturations 83-80% - start with 4 litres,
- Saturations 80-78% - start with 5 litres,

For saturations $< 78\%$, start with 6 litres and titrate up to and including 10 litres as required to achieve saturations of 90%, for at least half of the 6MWT duration, where possible.

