10.4 Baseline assessments and Randomization (Visit 2 in Week 0)

Following the run-in period at the baseline visit (visit 2), stability of respiratory symptoms will be assessed according to routine clinical care. Only patients with stable symptoms (no chest infections and no changes in medications) during four weeks before including the run in period will be assigned in random order to two weeks on ambulatory oxygen or not treatment for two weeks.

Patients will be invited to perform two 6MWTs, one on oxygen and one on air-filled canisters at the flow rate identified during the first session, in random order, with a rest of at least 20 minutes between tests. Oxygen flow rates to be provided to the patient will be determined during the screening visit on the basis of the 6MWT on O₂, as the flow needed to provide and to maintain optimal oxygen saturation ≥ 90% for at least half of the 6MWT duration, where possible, and/or a maximal flow of 10L/min (7).

The patient will be blind to the content of the canisters.

Patients will then be randomised as to the order in which they will receive the portable oxygen *versus* no oxygen for the first two weeks of the treatment period as outlined in Section 9.2.

The treatment period of the study will consist of a four week randomized crossover trial of ambulatory oxygen for use during physical activity. At Visit 2, eligible patients will be asked to:

- complete the K-BILD questionnaire(14) (see “primary outcome” section) and three other questionnaires (the Shortness of Breath Questionnaire (SOBQ) (15), St George’s Respiratory Questionnaire (SGRQ) (16), Hospital Anxiety and Depression Scale (HDAS) (18), see below section 10.5);
- Concomitant medication review;
- Adverse Event
- Pulse oximetry at rest on room air
- 6MWT one on oxygen at the optimal flow rate identified during the screening visit
- 6MWT on air

The two 6MWTs (one on oxygen the other on air cylinder) will be undertaken in random order, with a rest of at least 30 minutes between tests. The patient will be blind to the content of the canisters. 6MWT measured parameters will include 6-minute walk distance, oxygen saturation and heart rate measured continuously (WristOx2™ model 3150), Borg dyspnoea and Borg fatigue score before and at the end of the test, time to recovery of heart rate, oxygen saturation, Borg dyspnoea and Borg fatigue.

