- Provide a Sensewear armband for patients to wear during the second week (5+2 days) of each of the two week treatment periods;
- Provide oxymeter for patients to wear for 48 hrs during the second week of each two week treatment periods (on oxygen and on no oxygen);
- Supply a diary of daily activities and instructions on completion by patients during the two weeks until the next visit (Visit 3);
- Dispense treatment based on randomisation allocation.
- The next study visit will be set up within two weeks of the baseline visit.

10.5 Crossover Visit – Visit 3 in Week 2

At Visit 3, patients will be asked to:

- Pulse oximetry at rest on room air;
- Concomitant medication review;
- AE assessment;
- Global assessment of change in walking ability and breathlessness (18);

- Ask patients to submit daily activity diary relating to the previous two weeks, Sensewear armband given during the baseline visit (visit 2) and therefore related to the past two weeks;
- Ask patients to submit their 48 hrs oxymeter readings, provided at the baseline visit;
- Complete study questionnaires including K-BILD questionnaire (14), Shortness of Breath Questionnaire (SOBQ) (15), St George's Respiratory Questionnaire (SGRQ) (16), Hospital Anxiety and Depression Scale (HDAS) (18),
- Ask patients to complete diary of daily activities during the following two week treatment period until the next visit (visit 4);
- Provide Sensewear armband for patients to wear during the second week (5+2) of the two weeks of the final treatment period;
- Provide oxymeter for patients to wear for 48 hrs during the week when the Sensewear armband is worn;
- Cross-over to the alternative treatment.

10.6 End of Treatment Visit – Visit 4 in Week 4

At Visit 4, patients will be asked to undertake:

- Pulse oximetry at rest on room air
- Concomitant medication review
- AE assessment
- Global assessment of change in walking ability and breathlessness (19)
- Ask patient to submit daily activity diary, Sensewear armband, and 48 hrs oxymeter reading related to the final two week treatment;
- Complete study questionnaires including K-BILD questionnaire (14), Shortness of Breath Questionnaire (SOBQ) (15), St George's Respiratory Questionnaire (SGRQ) (16), Hospital Anxiety and Depression Scale (HDAS) (18).

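### The ±7-day visit window sets no minimum period length, so the two-week recall of the K-BILD can reach outside the treatment period it is meant to score and dilute the primary contrast

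*Protocol*

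**What the plan says.** Section 10.1 sets one general timing rule: "The scheduled study visits should occur at the specified week post-screening", with a tolerance of ± "7 days unless otherwise specified". The nominal times come from the section headings: "Screening assessments at Visit 1 (Week -2") for 10.2, "Baseline assessments and Randomization (Visit 2 in Week 0") for 10.4, "Visit 3 in Week 2" for 10.5 and "Visit 4 in Week 4" for 10.6.

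The same section 10.1 states the recall period of the primary instrument: "The K-BILD asks patients to rate the impact of their ILD in the previous 2 weeks". Section 10.9 has the K-BILD completed at screening, at baseline and at the end of each treatment period (Visits 3 and 4). The crossover takes place at Visit 3 (10.5). Section 6.1 states that no wash-out is needed because oxygen acts at once.

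The only rule on the gap between two treatment visits is in 10.4: "The next study visit will be set up within two weeks of the baseline visit". That is a ceiling on the first period. No corresponding rule is given for the second period, and no floor for either.

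**The concern.** The primary analysis (17.4.2) compares change from baseline on and off oxygen within patients. The baseline cancels, so the contrast is simply the Visit 3 score against the Visit 4 score. Each score is meant to describe one condition. It does so only if the 14 days before the visit lie inside one treatment period, or reach back into days under the same condition.

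The window is counted from screening and applies to each visit separately, so it controls calendar dates and not period length. If a period is cut short, the recall reaches back beyond its start. The missing wash-out rationale does not help here: an effect that stops immediately still counts in a score that looks back two weeks. The consequence is a primary contrast biased towards no effect, by an amount set by visit booking. An analysis can flag or drop questionnaires completed too early, but it cannot recover the answers that a full period would have given.

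**Working it through.** **The plan's own figure.** Section 17.3.1 gives 80 patients for 90% power to detect 8 points at 5%, with SD 20 and 15% drop-out. Take 20 as the SD of within-patient differences, with a two-sided paired t-test. Then 68 completers give 90.2% power, and 68/0.85 = 80. The figure reproduces, so 68 completers and SD 20 are used below.

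**Allowed visit days after screening** (nominal day ± 7):
- Visit 2: 14 ± 7 = days 7 to 21
- Visit 3: 28 ± 7 = days 21 to 35
- Visit 4: 42 ± 7 = days 35 to 49

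Period 1 can then last from 21 − 21 = 0 to 35 − 7 = 28 days, and period 2 from 35 − 35 = 0 to 49 − 21 = 28 days. The 10.4 ceiling cuts period 1 to 0–14 days and leaves period 2 at 0–28. One visit moved by the full 7 days gives a 7-day period. Zero days needs two adjacent visits at opposite limits.

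**Share of the recall inside the right period.** Assume recall weights all days equally, and let L be the period length: f = min(L, 14)/14.
- Air-first: the Visit 3 recall is off oxygen whatever the length of period 1, because the run-in is also off oxygen. The contrast is 8 × f2.
- Oxygen-first: a short period 1 lets run-in days into Visit 3, and a short period 2 lets oxygen days into Visit 4. The contrast is 8 × (f1 + f2 − 1). This is exact here, because Visits 2 and 4 are always at least 35 − 21 = 14 days apart.

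Example: with a 7-day second period and a full first period, f2 = 0.5 and 8 points becomes 4 in either sequence.

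**Scatter scenarios.** Let each visit fall uniformly and independently within ±w days of its nominal day. The mean shortfall of a period below 14 days is m = Σ k(2w + 1 − k)/(2w + 1)², summed over k = 1 to 2w. The mean contrast is 8(1 − m/14) in air-first and 8(1 − 2m/14) in oxygen-first patients. With equal sequence sizes the average is 8(1 − 1.5m/14).

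| Scatter | m (days) | Oxygen-first | Air-first | Average | Power, n = 68 |
|---|---|---|---|---|---|
| none | 0 | 8.0 | 8.0 | 8.0 | 90% |
| ±1 day | 4/9 = 0.44 | 7.5 | 7.7 | 7.6 | 87% |
| ±2 days | 20/25 = 0.80 | 7.1 | 7.5 | 7.3 | 84% |
| ±3 days | 56/49 = 1.14 | 6.7 | 7.3 | 7.0 | 81% |
| ±7 days | 560/225 = 2.49 | 5.2 | 6.6 | 5.9 | 66% |

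Power is for the average contrast, with the SD of differences held at 20.

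**With the 10.4 ceiling applied**, the average hardly moves: ±7 days gives 5.9 points and 67%, and ±3 days gives 7.1 points and 82%. Under ±7 days, second periods shorter than 14 days fall from 47% to 31%, but first periods become shorter.

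**The case against.** The strongest reply is that the window does not stand alone. It yields to anything specified otherwise, and the protocol describes two weeks on and two weeks off oxygen many times (for example 5.1, 6.1, 6.1.4 and 10.9). Sections 10.4 and 10.5 place the armband in the second week of each period, and 10.4 does the same for the oximeter. Section 15.3 has missed monitoring made up over the following week. A period of 0 to 7 days has no second week. A reader might infer from 10.1 that such periods are fully compliant; the documents do not support that, because the other sections contradict it. This part of the objection stands. It leaves periods of about 8 to 13 days, which lie inside the window and for which no minimum is stated.

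A reader might also infer that the trial will lose a quarter of its power or more. That does not follow either. The 66% needs visits spread evenly over the whole window, and a uniform 7-day second period (4 points, 37% power) needs every patient to be at an extreme. The protocol gives no distribution of visit days. Delays carried forward from one visit to the next would keep the 14-day gaps, and if patients give recent days more weight the dilution is smaller.

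Finally, 17.3.1 does not say which SD the 20 is. If it were a between-patient SD combined with the quoted intra-class coefficient of 0.94, the SD of differences would be 20 × √(2 × 0.06) = 6.9. Even a 4-point contrast would then have more than 99% power at n = 68. That would remove the power loss but not the bias in points, which matters when the result is read against an 8-point minimal important difference. It would also not reproduce the stated 80 patients.

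Counting from screening is not the whole cause. With ±7-day windows counted from Visit 2, period 1 would be at least 7 days but period 2 could still be 0.

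**Conclusion.** The point holds as a timing fault that should be fixed. It does not show that the trial is underpowered. The visit window, the two-week periods and the two-week recall are not reconciled, and nothing prevents a K-BILD from being completed before its recall fits inside the period. The dilution affects Visit 4 in both sequences and Visit 3 only in oxygen-first patients, so it is larger in that sequence. Its direction is towards no effect: the risk is a missed or understated benefit, not a false one.

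For visit scatter of ±1 to ±3 days the loss is about 0.4 to 1.0 of 8 points, and about 3 to 9 percentage points of power. Full uniform use of the window marks the upper scenario at about 2.1 points lost. These sizes rest on equal weighting of recall days, independent uniform visit days, equal sequence sizes and 20 as the SD of within-patient differences. The fault in the timing rules needs none of these assumptions.

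**What to change.** In 10.1, keep ±7 days for Visit 2 only. Time the Visit 3 and Visit 4 K-BILD from the start of the current period: not before day 14 of that period, with a short tolerance on the late side only, so that the recall lies within one period. Reword the 10.4 sentence on booking Visit 3, since a ceiling of two weeks combined with a floor of day 14 would leave a single permitted day. Check the result against the second-week monitoring in 10.4 and 10.5.

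The cost is protocol wording and slightly less freedom for sites in booking Visits 3 and 4. A sensitivity analysis by actual period length is optional and can be left to the SAP.
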